12.1.2 Sample Size Determination

Since this is a feasibility study, the overall sample size was selected based on a combination of regulatory, logistical, and statistical considerations. While formal hypothesis testing for the primary effectiveness endpoint is not expected to be conclusive, the analysis of change in LBG is expected to provide more power as it is based on a continuous outcome. An assessment of the planned sample size based on this endpoint follows.

Sample size was determined based on a two-sided two sample unequal variance t-test with an overall 5% significance level for comparison of [REDACTED] GFeBGS versus Active control using the following assumptions:

- 1:1 randomization for GFeBGS and Active control (equal allocation of subjects to the control and each of the three treatment group separately, $n_1=n_2=n_3=n_4$ resulting in a 1:1:1:1 randomization allocation)
- Power = 80% for the secondary effectiveness endpoint of LBG
- $\delta = 1.70$ mm mean advantages in the change from baseline in LBG to be tested in favor of GFeBGS (3.00 mm) versus Active control (1.30 mm)
- Corresponding standard deviations (SDs) are projected to be 1.20 and 2.30 mm for the GFeBGS and Active control groups respectively
- 15% dropout rate by 6 month post-surgery.

With a minimum of 20 patients per treatment group, the power is at least 80% to detect a difference of 1.70 mm based on a two sample unequal variance t-test.

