12.1.5 Patient and Visit Deviations

Patients will be evaluated to assess eligibility, treatment compliance, visit compliance, and other protocol deviations such as excessive smoking, poor dental care, concurrent medical conditions impacting effectiveness or safety evaluations, and missed visits. Any post-baseline visits occurring more than two weeks outside of study visit windows will be reported. Withdrawals due to lack of effectiveness or adverse events will also be reported as well as the timing of such events. Dropouts will also be reported as well as the nature and timing of such dropouts for any reason. A 15% allowance has been made for dropouts; treatment assignments for dropouts will not be recycled. All patients will be included in all analyses to the fullest extent possible; no data will be carried forward.

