12.1.7 Missing Data Strategies

Given the nature of the study, very few dropouts (<5%) are expected. This is a consequence of the close bond that develop between study Investigator teams and their patients, which will be observed and reinforced through the Study Monitors assigned to respective sites. In the event that there are any missing data, the percents with missing data will be compared using a two-sided Fisher Exact test; the reason for withdrawal will be presented to see if any treatment group or site pattern exists. While the primary analysis will be based on all available data with no imputation performed, sensitivity analyses will be performed to assess the potential impact of missing data.

This will include an analysis where missing data is treated as a success, an analysis where missing data is treated as a failure, and finally an analysis where missing data in the control group is treated as a success and missing data in the GFeBGS group is treated as a failure.

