12.1.9 Secondary Effectiveness Analysis

Superiority will be tested for the continuous effectiveness endpoints (e.g. Δ CAL, LBG, %BF, PD) using an ANCOVA model with the same baseline covariates as specified above and in addition, the corresponding baseline value for each endpoint. The ANCOVA model will include the same covariates as for the primary effectiveness endpoint. The two-sided 95% lower bound for the LSMEAN difference between each of the three GFeBGS treatment groups minus Active control will need to exceed 0 to achieve superiority.

Additional ANCOVA models will also evaluate any additional covariates found to be imbalanced ($p \leq 0.05$) at baseline.

Effectiveness outcomes will be displayed at every visit in order to characterize the time of onset and duration of effectiveness throughout the study. Results will be displayed for subjects who complete the study as planned as well as for those withdrawn early; the patterns of withdrawal will be displayed for each study treatment group to assess if reasons withdrawn were different in any respect.

Analyses will also be conducted for the other effectiveness endpoints inclusive of PDR, GR, WH, and BOP; the second composite endpoint (Δ CAL, %BF) will be analyzed in the same manner as for the first composite endpoint. In general, for continuous variables, the mean, median, standard deviation, minimum and maximum values will be displayed; for ordinal and categorical variables,

CONFIDENTIAL

frequencies and percentages will be displayed. When relevant, the mean changes from pre-operative baseline will be computed for all treatment groups at each visit through study exit; an unpaired t-test will be used to test for improvement between the treatment groups while a paired t-test will be used to test for improvement within the treatment groups. Superiority will be tested for continuous outcomes using an unpaired t-test by examining the two-sided 95% lower bound for the difference between GFeBGS minus Active control to test if the lower bound exceeds 0. The percents achieving predefined effectiveness milestones will be displayed at each post-baseline time through each stage; a two-sided Fisher Exact test will be used to test for superiority.

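### The planned six-month comparisons of attachment, probing depth and recession leave 3-month values unused, and the listed missing-data checks do not cover the continuous endpoints

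*Protocol*

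**What the plan says.** - **Missing data (12.1.7).** "While the primary analysis will be based on all available data with no imputation performed". Three checks follow, beginning: "This will include an analysis where missing data is treated as a success". The second treats missing as failure. The third sets missing to success in control and failure in GFeBGS. The percentages missing are compared by Fisher's exact test. Section 12.1.5 also rules out carrying data forward.
- **Continuous endpoints (12.1.9).** CAL change, LBG, %BF and PD are tested "using an ANCOVA model with the same baseline covariates as specified above", plus the endpoint's own baseline value. Unpaired t-tests are also planned. No visit term or within-subject covariance is mentioned.
- **Primary composite (12.1.8).** Logistic regression with age and smoking, and an exact interval.
- **Visits (8.3.6).** PD, GR, calculated CAL and a standardized radiograph are obtained at both 3 and 6 months. The same visit procedures serve early termination.
- **Dropout.** Section 12.1.5: "A 15% allowance has been made for dropouts". Sections 5.1 and 12.1.2 also use 15%, but 12.1.7 expects fewer than 5%.
- **Sizing (12.1.2).** "Power = 80% for the secondary effectiveness endpoint of LBG".

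**The concern.** A subject who attends month 3 but has no six-month value adds nothing to a six-month ANCOVA or t-test, although the 3-month CAL, PD and GR are in the database. If subjects with poor early response leave more often, those who remain are a selected group, and the selection need not be equal across arms.

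The protocol does not treat loss as unrelated to outcome. Section 6.4 lists discontinuation for rescue treatment of the target tooth and for loss of the device, and 12.1.5 plans to report withdrawals for lack of effectiveness.

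The listed checks would not show the effect on measurements in millimetres, because success and failure fills are undefined for them. Section 12.1.2 says the test of the composite is not expected to be conclusive and looks to LBG for power. The most informative endpoint therefore has no listed missing-data check. Comparing percentages missing is a weak safeguard: with 23 per arm, Fisher's test has about 9% power to detect 20% against 10% missing.

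**Working it through.** **1. The plan's own figure.** Inputs from 12.1.2: difference 3.00 - 1.30 = 1.70 mm; SDs 1.20 (GFeBGS) and 2.30 (control); two-sided 5%; unequal-variance t-test.

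- Standard error at 20 per arm: sqrt(1.20²/20 + 2.30²/20) = sqrt(0.0720 + 0.2645) = 0.580 mm.
- Noncentrality: 1.70/0.580 = 2.93. With Satterthwaite degrees of freedom, power is 0.808 (0.786 at 19 per arm). The stated 80% with 20 per arm reproduces.
- Dropout: 94 × 0.85 = 79.9, matching the 80 evaluable. At 5%, 94 × 0.95 = 89.3.

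Sizing already absorbs a 15% loss, so the issue is bias, not power.

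**2. Bias in the LBG difference.** The protocol gives neither the correlation between the two visits (ρ) nor the dropout mechanism. Assumed: ρ from 0.3 to 0.9; 3-month mean equal to 60% of the six-month mean; the same SD at both visits within an arm; log-odds of dropout rising by 1 per mm of poorer response. Large-sample simulation, 300,000 per arm. The plain six-month completer difference is compared with the likelihood estimate, which in each arm is

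completer mean + b × (3-month mean of all subjects - 3-month mean of completers),

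where b is the within-arm regression slope of month 6 on month 3. This corresponds to a repeated-measures model with covariance estimated by arm.

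| Dropout depends on | Rate (control/active) | Completers: bias in mm, ρ = 0.3, 0.5, 0.7, 0.9 | Using month 3 |
|---|---|---|---|
| nothing | 15/15% | about 0 | about 0 |
| 3-month value | 5/5% | -0.03, -0.06, -0.09, -0.11 | about 0 |
| 3-month value | 15/15% | -0.10, -0.16, -0.21, -0.28 | about 0 |
| 3-month value | 20/10% | -0.16, -0.26, -0.36, -0.46 | about 0 |
| unseen 6-month value | 5/5% | -0.11, -0.12, -0.13, -0.13 | -0.10, -0.09, -0.07, -0.03 |
| unseen 6-month value | 15/15% | -0.31, -0.31, -0.31, -0.32 | -0.29, -0.25, -0.19, -0.08 |
| unseen 6-month value | 20/10% | about -0.51 throughout | -0.48, -0.42, -0.31, -0.13 |

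A hand check: selecting directly on the six-month value at 15% shifts the difference by -0.31 mm. Selecting on the 3-month value passes on a fraction ρ of that: 0.5 × -0.31 = -0.16 and 0.8 × -0.31 = -0.25. Against the standard error, 0.16/0.580 = 0.27 and 0.25/0.580 = 0.43.

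Bias appears even at equal dropout rates because the control SD is larger, so the same selection moves the control mean further.

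**3. CAL change, PDR and recession change.** The protocol gives no means or SDs for these, so no figure in mm is possible. With equal SDs and equal dropout in both arms the two shifts cancel. With SD 1, 23 per arm, ρ 0.5-0.8, 12% missing overall and poor responders leaving mainly from control, the completer bias is -0.11 to -0.18 SD, and about 0 once month 3 is used.

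**4. Precision.** If every leaver has a 3-month value, effective n per arm at 15% dropout is 23.5 × 0.85/(1 - 0.15ρ²). That is 19.975/0.9865 = 20.2 at ρ = 0.3 and 19.975/0.8785 = 22.7 at ρ = 0.9. Power moves from 0.81 to between 0.81 and 0.86. This is a ceiling.

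**The case against.** Much can be said for the plan as written. Baseline-adjusted ANCOVA is standard. The list of sensitivity analyses is introduced as what will be included, so an SAP could add to it. This is a feasibility study without tests for approval or labeling, and dose selection (12.1.10) rests on the binary composite, which a linear repeated-measures model does not touch. The sentence on no imputation concerns that composite. All of this stands and keeps the point small. It does not change the fact that 12.1.9 fixes a method that leaves collected data unused, while 12.1.5 promises to include all patients as fully as possible.

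Whether leavers truly contribute nothing is also not settled. Figure 5 and 8.3.6 make Visit 9 both the six-month and the early-termination visit, 6.5 asks for that visit to be attempted, and 10.2 codes out-of-window visits to the closest window. Some early-termination values may therefore enter as six-month data. The protocol does not say.

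The size rests on assumed correlations and mechanisms, and the comparator is an unadjusted completer difference rather than the planned ANCOVA. The bias at 15% is under half a standard error. If the <5% expectation in 12.1.7 holds, it is about 0.1 mm or less.

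A reader might infer that a repeated-measures model removes dropout bias outright and needs no further data. The documents do not support either. Removal requires dropout to be missing at random given the observed values. For LBG, 5.2.2 has only baseline and six-month films assessed, while 5.2.3 has the 3-month films analysed for bone growth too, so 3-month LBG may not exist.

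**Conclusion.** The point holds as a cheap improvement. The planned six-month ANCOVA and t-tests for CAL change, PDR and recession change ignore the 3-month values of subjects without a six-month value, and the listed sensitivity analyses cannot be applied to LBG or CAL change in mm.

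For dropout explained by the 3-month response, the bias avoidable in LBG is about 0.15-0.25 mm of 1.70 mm at 15% dropout and about 0.1 mm or less at 5%, for assumed correlations of 0.5-0.8. For LBG this benefit also requires the 3-month films to be measured. Where dropout depends on the unseen six-month value, much of the bias remains: at 15% and correlation 0.5, -0.25 of -0.31 mm. Where dropout is completely at random there is nothing to correct. Subjects who leave before month 3 add little.

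Two further inferences should be resisted. Completer analysis does not take LBG power below 80%. Nor is the missing-at-random assumption bracketed by the existing worst-case fill, because that fill is not defined for the continuous endpoints.

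**What to change.** 1. **12.1.9:** analyse CAL change, PDR and recession change with one repeated-measures model over 3 and 6 months: treatment by visit, unstructured covariance, the same covariates and the baseline value. Report the six-month contrast. This still uses all available data without imputation.
2. **12.1.7:** add a multiple-imputation sensitivity analysis of six-month CAL change and LBG from baseline and 3-month values, within arm, dichotomised afterwards for the composite. Use 3-month LBG if those films are measured, and reconcile 5.2.2 with 5.2.3 on this.
3. **Dropout:** state one assumption in place of 15% (5.1, 12.1.2, 12.1.5) and <5% (12.1.7).
4. **Early termination:** state whether Visit 9 measurements taken at early termination count as six-month values, and how 10.2 applies to them.

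Cost: wording and some programming. No new clinical measurement is needed for CAL, PD or GR. For LBG, the 3-month films must be read if they are not already. The price is a missing-at-random assumption that should be stated openly, since no existing check on the continuous endpoints tests it.

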12.1.8 Primary Effectiveness Analysis

Comparisons will be made between the control group and each of the treatment groups using 2x2 tables. Superiority for the composite endpoint will be tested using a logistic regression model to include age (< 50 versus \geq 50 years) and smoking status (never or not within the last 6 months vs. any within the last 6 months) at the time of randomization as the baseline covariates. The two-sided 95% lower bound for the LSMEAN difference for each of the three GFeBGS treatment groups minus the Active control will need to exceed 0% to achieve superiority. An unadjusted logistic regression model for the primary composite endpoint will also be performed.

Superiority will also be tested using an exact two-sided 95% lower confidence bound for the difference in success percents. The two-sided 95% lower bound for each of the three GFeBGS treatment groups minus Active control difference must be \geq 0% to achieve superiority.

Additional logistic regression models will also evaluate any additional covariates found to be imbalanced ($p \leq 0.05$) at baseline.

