| Study Design: This will be a prospective, randomized, double-blinded, controlled, multi-center, dose-verification clinical study in subjects who require surgical intervention to treat a qualifying periodontal defect. Treatment randomization will be stratified by smoking status. The parallel arms will be: Treatment I: β -TCP alone (active control) Treatment II: [REDACTED] GFeBGS: consisting of β -TCP and 0.1% rh-bFGF Treatment III: [REDACTED] GFeBGS: consisting of β -TCP and 0.3% rh-bFGF Treatment IV: [REDACTED] GFeBGS: consisting of β -TCP and 0.4% rh-bFGF After signing an informed consent for screening, being screened, having pre-surgical treatment and baseline measurements, signing an informed consent for study enrollment, subjects meeting inclusion criteria and not meeting any exclusion criteria will be randomized to one of four groups so that treatment is balanced within each investigational site and according to smoking status. Enrollment will be defined as randomization to one of the above-mentioned study arms. Investigators who perform evaluations will remain blinded to the investigational device implantation of all subjects for the 6-months post-surgery. The roles of Investigator will be determined at the start of the study and will remain until completion of the study. The study will be conducted in accordance with the Declaration of Helsinki (1996) and Good Clinical Practices (GCPs). The study will receive IRB approval at each investigational site prior to commencement of the study. Investigators will administer treatments to subjects following pre-surgical procedures, and subjects will receive surgical implantation of the investigational device or the active control in the intrabony periodontal defect located at the target tooth having pocket depths (PD) \geq 7 mm and vertical bone defect \geq 4 mm with at least 1 defect wall. Wound-healing (WH) scale of the surgical site will be examined at 2 and 4 weeks post-surgery. Clinical examinations, clinical attachment level (CAL), probing depth (PD), gingival recession (GR) and bleeding on probing (BOP), of the treated tooth will be performed at 3 and 6 months. Radiographic examination will also be performed at baseline, 3 and 6 months. After all subjects complete the 6-month follow-up post-surgery, the data will be assessed to select the optimal therapeutic rh-bFGF dose. Primary Objective: To obtain dosing data on [REDACTED] Growth Factor enhanced Bone Graft Substitute (GFeBGS) for the | |

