5.0 STUDY DESIGN AND DESCRIPTION

5.1 Study Design

This will be a prospective, randomized, double-blinded, controlled, multi-center, dose-verification clinical study in subjects who require surgical intervention to treat a qualifying periodontal defect. A total of 94 subjects will be randomized to obtain at least 80 evaluable subjects in anticipation of a 15% dropout rate. This study will be conducted in six sites in the United States.

The duration of the study for each subject will be six months following implantation of the study device.

Subjects will participate in a Screening Period lasting up to 2.5 months. Subjects must have been diagnosed to have at least one periodontally related osseous defect to be treated by periodontal reconstructive surgery. Subjects must be systemically healthy and not have any sites suffering from localized juvenile periodontitis. Subjects must not partake in the daily use of smokeless chewing tobacco, pipe or cigar smoking, or smoke more than 10 cigarettes a day or the equivalent.

After a successful screening, eligible subjects will be randomized using variable block sizes for the four treatment groups. The study will be stratified to control for potential differences in healing rates and responses in the treatment based on smoking habits (between non-smokers and moderate smokers).

The treatment groups are:

Treatment I: β -TCP alone (active control)

Treatment II: [REDACTED] GFeBGS: consisting of β -TCP and 0.1% rh-bFGF

Treatment III: [REDACTED] GFeBGS: consisting of β -TCP and 0.3% rh-bFGF

Treatment IV: [REDACTED] GFeBGS: consisting of β -TCP and 0.4% rh-bFGF

Subjects will be evaluated at 2 and 4 weeks and 3 and 6 months following surgery (see Figure 5).

Figure 5 Schematic of Study Visits and Windows

| | Screening period | Pre-treatment procedures | | | Treatment/ Post-treatment follow-up period | | | | |
|-----------|------------------|---------------------------------------|---------------|----------|--|--------------|--------------|--------------|---------------------------------|
| Visit # | Visit 1 | Visit 2 | Visit 3 | Visit 4 | Visit 5 | Visit 6 | Visit 7 | Visit 8 | Visit 9 |
| Procedure | Screening | Pre-treatment | Pre-treatment | Baseline | Surgery | Wk 2 | Wk 4 (1 Mo) | 3 Mo (12 Wk) | 6 Mo/ Early termination (24 Wk) |
| Schedule | <-3 Mo | -2 Mo (\geq 2Wks before Baseline)* | -2 Wks | | | | | | |
| Windows | | (-2 days)* | | Day 1 | \pm 3 days | \pm 3 days | \pm 7 days | \pm 7 days | |

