5.2 Justification for Study Design and Endpoints

5.2.1 Study Design

The randomization of the investigational device kits will be performed by [REDACTED] for the allocation of subjects at each investigational site. Subjects will be randomized to one of four groups so that treatment is balanced within each center by block randomization method stratified by smoking status. Enrollment will be defined as randomization to one of the above-mentioned study arms (Treatment I ~ IV). The randomization will be performed intraoperatively after surgeons confirm if the probing bone depth and the number of bony wall of defect of the target site meets the inclusion criteria (greater than 4 mm and at least one bony wall).

The active control arm (β -TCP alone) will be used for comparisons to three test groups with different rh-bFGF concentrations (0.1%, 0.3% and 0.4%) in order to determine the optimal concentration of rh-bFGF in combination with β -TCP to treat a qualifying periodontal defect.

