7.2 Randomization Code Creation and Storage

The investigational device kits are assembled by a clinical supplies vendor [REDACTED] [REDACTED] and are visually identical. The randomization code will be created by [REDACTED] as the Sponsor's designee. Block randomization will be stratified by smoking status (non-smoker or smoker). The randomization schedule will be provided to the Investigator as a list of sequential product numbers on the label of the carton box

assigned by [REDACTED]. In the event that devices must be disposed of, replacement devices will be made available.

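### Treatment is said to be balanced within site, but the primary composite analyses leave site out; if sites differ, the log-odds test becomes conservative and loses some power

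*Protocol*

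**What the plan says.** **Randomization.** The summary (Section 1.0) has subjects "randomized to one of four groups so that treatment is balanced within each investigational site and according to smoking status". Section 5.2.1 says that "treatment is balanced within each center by block randomization method stratified by smoking status". Section 7.2 says "Block randomization will be stratified by smoking status (non-smoker or smoker") and does not mention site. The stratification sentence in Section 5.1 also names smoking alone.

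**Primary analysis (Section 12.1.8).** "Superiority for the composite endpoint will be tested using a logistic regression model to include age" (below 50 versus 50 and over) and smoking status. The decision rests on "The two-sided 95% lower bound for the LSMEAN difference for each of the three GFeBGS treatment groups minus the Active control", which must exceed 0%. An unadjusted logistic model is added, and "Superiority will also be tested using an exact two-sided 95% lower confidence bound for the difference in success percents". None of these uses site. Further covariates enter only if found imbalanced at baseline at p of 0.05 or less.

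**Size.** "This study will be conducted in six sites in the United States". "A total of 94 subjects will be randomized to obtain at least 80 evaluable subjects in anticipation of a 15% dropout rate".

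**Status.** Section 12.1.1 describes the tests as internal, and Section 12.1.2 does not expect the composite test to be conclusive.

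**The concern.** The choice of covariates does not follow the design. Smoking is a stratifier and is in the model. Age is never described as a randomization factor, yet it is in. Site, on which Sections 1.0 and 5.2.1 say allocation is balanced, is out. The imbalance rule is unlikely to bring it back, because blocking within site makes a significant site imbalance unlikely.

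Blocking removes between-site differences from the treatment contrast. A model without site still counts them as noise, so its standard error is too large whenever sites differ. They could differ here: under Section 8.2.1 each site has one or two surgeons, and one of them should do most of the procedures, so site nearly coincides with surgeon. What is at stake is precision in a trial with about 20 evaluable subjects per arm.

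**Working it through.** **1. The plan's own figure.** Section 12.1.2 gives power for LBG, not for the composite: 20 per arm, difference 1.70 mm, SDs 1.20 and 2.30 mm, two-sided 5%, unequal-variance t-test.

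- SE = sqrt((1.20² + 2.30²)/20) = sqrt(6.73/20) = 0.580 mm
- Noncentrality = 1.70/0.580 = 2.93, with Satterthwaite df 28.6
- Power from the noncentral t = 80.8%, against the stated figure of at least 80%
- Dropout: 94 × 0.85 = 79.9, in line with 80 evaluable

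The figure reproduces. This point does not affect it, because it concerns a different endpoint and test.

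**2. How thin the strata are.** 80/4 = 20 per arm. 20/6 = 3.3 per arm per site. Crossing site with smoking gives 12 strata and 20/12 = 1.7 per arm per stratum.

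**3. Simulation A, one dose against control.** 4,000 trials per setting; Monte Carlo SE is about 0.35 points at 5% and 0.8 points for power. From the protocol: 94 randomized, 15% dropout, six sites, 1:1:1:1, blocks within site and smoking, two-sided 5%. Assumed: 35% control success, log odds ratio 1.4 (odds ratio about 4), 25% smokers, between-site logit SD from 0 to 1.5.

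| Site SD (logit) | 0 | 0.5 | 1.0 | 1.5 |
|---|---|---|---|---|
| Type I %, log-odds Wald, no site (planned) | 4.9 | 4.0 | 3.4 | 2.5 |
| Type I %, percent-scale difference, no site | 7.2 | 6.0 | 5.5 | 4.2 |
| Type I %, percent-scale difference, five site indicators | 8.3 | 7.7 | 8.5 | 8.0 |
| Type I %, CMH by site | 4.5 | 4.7 | 4.4 | 4.4 |
| Power %, log-odds Wald, no site (planned) | 55.9 | 50.5 | 42.9 | 32.6 |
| Power %, CMH by site | 54.0 | 50.3 | 47.1 | 40.4 |
| CMH minus planned, points | -1.9 | -0.2 | +4.2 | +7.8 |

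With 50% success under the null, the planned log-odds test has type I error of 5.3, 4.9, 3.7 and 2.4%, the same pattern.

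**4. Simulation B, random site intercept.** 80 evaluable, six sites, 40% control success, odds ratio 4, same SD range.

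| Site SD (logit) | 0 | 0.5 | 1.0 | 1.5 |
|---|---|---|---|---|
| Type I %, planned log-odds Wald | 4.3 | 4.7 | 3.6 | 2.4 |
| Type I %, with random intercept | 4.6 | 5.0 | 4.5 | 4.0 |
| Power %, planned | 56 | 52 | 42 | 31 |
| Power %, with random intercept | 56 | 52 | 46 | 37 |
| Gain, points | 0 | 0 | 4 | 6 |

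**5. Reading the rows.** Power falls with SD for every method, partly because a fixed odds ratio gives a smaller percent difference when sites vary (35% v 68% at SD 0, 36% v 60% at SD 1.5 in simulation A). Only the gap between methods at the same SD is due to omitting site.

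**6. What the SDs mean.** Around 40% success the logit is -0.405. One SD either side gives about 29% to 52% at SD 0.5, 20% to 64% at 1.0, and 13% to 75% at 1.5.

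**7. Other site adjustments** (40% control, odds ratio 4, SD 0 / 0.5 / 1.0 / 1.5).

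- Exact conditional logistic regression by site: type I error 2.1 / 1.6 / 2.2 / 1.5%; power 40 / 36 / 34 / 26%, against 54 / 49 / 42 / 29% for the unadjusted Wald test.
- Mantel-Haenszel risk difference by site: type I error about 6 to 7% with the Sato variance, 11 to 13% with the Greenland-Robins variance. Stratified by smoking as well: 7 to 8% and 18 to 19%.

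**The case against.** The strongest reply is that the loss is hypothetical. The protocol gives no between-site variation and no composite success rates. It also works against site differences: examiners are calibrated to a gold standard (Section 8.2.2), surgeons are trained to one technique (8.2.1), and LBG is read at one center (8.1.3.3). An SD of 1.5 is then hard to believe. This stands, and it is why the size can only be given as a range starting at zero. Calibration and central reading reduce measurement differences, however, and need not remove surgical ones.

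The second reply is that Section 12.1.8 decides on an LSMEAN difference against 0%, which suggests a percent scale. There, on one reading (a standardised risk difference), the model without site has type I error of 5.5 to 7.2% up to SD 1.0 and falls below 5% only at SD 1.5. This also stands. A reader might infer that omitting site always makes the primary test conservative and always costs power. The documents do not support that: it depends on sites differing and on the scale of the test.

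The third reply is low stakes. The tests are internal, the composite test is not expected to be conclusive, and Section 1.0 lets the sponsor take any of the three doses forward. This limits the weight of the point without removing it, because Section 12.1.10 bases dose selection on the same endpoint. A reader might infer that the dose choice is distorted; that was not calculated and is not claimed.

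Finally, Section 7.2 is silent on site, so site blocking is not beyond doubt. That is a reason to reconcile the sections.

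**Conclusion.** The point holds in a conditional form. The protocol states balance within site in two places, and every primary comparison fixed in Section 12.1.8 omits site. If success rates differ between sites, the log-odds test falls below its nominal level (about 3.5% at SD 1.0 and 2.5% at SD 1.5). Its power loss against a site-aware test is nil at SD 0, at most about 1 point at 0.5, about 4 at 1.0 and 6 to 8 at 1.5. On the percent scale it is not conservative until site differences are large.

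These sizes rest on the assumed SD range, control success of 35 to 40% and an odds ratio of about 4, none of which the protocol gives. The omission does not inflate the log-odds type I error. Nor would any site adjustment do: several common ones perform worse than the plan at this sample size. The point is worth correcting because the correction is cheap, but it does not threaten the study.

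**What to change.** 1. State in Sections 1.0, 5.1, 5.2.1 and 7.2, in the same words, whether site is a stratification factor.
2. If it is, add site as a random intercept to the logistic model with age group and smoking in Section 12.1.8. In simulation B this held its level and lost nothing when sites did not differ. Say whether the LSMEAN difference is on the log-odds or percent scale; the random-intercept results above are for log-odds, and a percent-scale bound from that model was not calculated.
3. The alternative is a site-stratified CMH test for each dose against control. It leaves out age and smoking, and it is a test, so the superiority rule written as a lower bound would need rewording.
4. Keep the model without site and the 2x2 comparison as supportive.
5. Do not make five fixed site indicators, exact conditional logistic regression or site-by-smoking strata the primary method at about 20 per arm. The indicators take type I error to about 8% on the percent scale, exact conditional regression loses power at every SD, and the crossed strata are too thin.

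The cost is wording and a slightly more complex model; no data, subjects or visits change. With CMH, up to about 2 points of power are given up against the log-odds test if sites do not differ, and a site with one of the two arms empty contributes nothing.
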